9.2.3. Event Causality Assessment

AEs will be assigned a relationship (causality) to the study treatment. The Investigator will be responsible for determining the relationship between an AE and the study treatment. The type of event, organ system affected, and timing of onset of the event will be factors in assessing the likelihood that an AE is related to the study treatment. Relationship of AEs to study treatment will be classified as follows:

- 1. Definitely related:** This category applies to those AEs that the Investigator feels are incontrovertibly related to the study treatment. An AE may be assigned an attribution of definitely related if or when it meets all of the following criteria: (1) it follows a reasonable temporal sequence from administration of the study treatment; (2) it could not be reasonably explained by the known characteristics of the participant's clinical state, environmental or toxic factors, or other modes of therapy administered to the participant; (3) it follows a known response pattern to treatment with the study treatment.
- 2. Probably related:** This category applies to those AEs which, after careful medical consideration at the time they are evaluated, are felt with a high degree of certainty to be related to the study treatment. An AE may be considered probable if or when (must have three): (1) it follows a reasonable temporal sequence from administration of the study treatment. (2) It could not readily have been produced by participant's clinical state, environmental or toxic factors, or other therapies administered to the participant. (3) Disappears or is decreased upon discontinuation of the study treatment. (4) It follows a known response pattern to treatment with the study treatment.
- 3. Possibly related:** This category applies to those AEs which, after careful medical consideration at the time they are evaluated, are judged unlikely but cannot be ruled out with certainty to the study treatment. An AE may be considered possible if or when (must have two): (1) it follows a reasonable temporal sequence from administration of the study treatment. (2) It could not readily have been produced by participant's clinical state, environmental or toxic factors, or other therapies administered to the participant. (3) Disappears or is decreased upon discontinuation of the study treatment. (4) It follows a known response pattern to treatment with the study treatment.

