- 4. Unlikely related:** In general, this category can be considered applicable to those AEs which, after careful medical consideration at the time they are evaluated, are judged likely to be unrelated to the study treatment. An AE may be considered unlikely if or when (must have two): (1) it does not follow a reasonable temporal sequence from administration of the study treatment. (2) It could not readily have been produced by participant's clinical state,

environmental or toxic factors, or other therapies administered to the participant. (3) Disappears or is decreased upon discontinuation of the study treatment. (4) It does not follow a known response pattern to treatment with the study treatment.

5. **Unrelated:** This category applies to those AEs which, after careful consideration at the time they are evaluated, are clearly and incontrovertibly due to extraneous causes (disease, environment, etc.) and determined with certainty to have no relationship to the study treatment.

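### Two of the four 'Unlikely related' criteria in protocol 9.2.3 were left un-negated, so evidence for drug causality counts toward 'Unlikely'

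*Protocol*

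**What the plan says.** Protocol 9.2.3 defines five causality categories. Probably (three items needed) and Possibly (two needed) share four items, all pointing toward the drug: fitting timing, no ready alternative cause, improvement on stopping, and a known response pattern. Items 3 and 4 there read "3) Disappears or is decreased upon discontinuation of the study treatment. (4) It follows a known response pattern to treatment with the study treatment".

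Unlikely starts "An AE may be considered unlikely if or when (must have two): (1) it does not follow a reasonable temporal sequence". Its item 2 starts "It could not readily have been produced by", as in the two higher categories. Its items 3 and 4 read "3) Disappears or is decreased upon discontinuation of the study treatment. (4) It does not follow a known response pattern to treatment".

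The opening judgements are "are judged unlikely but cannot be ruled out with certainty to the study treatment" for Possibly and "are judged likely to be unrelated to the study treatment" for Unlikely. The investigator makes the assessment, and 9.2.3 adds: "The type of event, organ system affected, and timing of onset of the event will be factors in assessing the likelihood".

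SAP 4.3.1 sends the reader to protocol 9.2.3 for these definitions. It counts Definitely, Probably and Possibly as treatment-related, and so leaves Unlikely and Unrelated out.

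**The concern.** An item that argues for the drug should not help to place an event in the category below the related/not-related cut. Reversing items 1 and 4 while leaving 2 and 3 as they were looks like incomplete editing, and neither document gives a reason for it.

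Three things depend on that cut:

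- The incidence of treatment-related events, one of the eight safety parameters listed in protocol 2.2.1.
- The treatment-related tables and listing in SAP 7.4.2.
- Dose-escalation stopping criteria a to f in protocol 3.1, each of which needs at least a 'possibly related' judgement.

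Cohorts have 8 or 10 participants and some criteria turn on a single event, so one label can matter.

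**Working it through.** The documents give no figure on this point, so there is none to reproduce. The check sets the lists side by side and then runs every combination of items through them.

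| Item | Probably and Possibly | Unlikely |
|---|---|---|
| 1 Timing | fits | does not fit |
| 2 Other ready cause | none | none (not reversed) |
| 3 On stopping | goes or lessens | goes or lessens (not reversed) |
| 4 Known response pattern | follows | does not follow |

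**Coding.** T = timing fits, N = no other ready cause, D = improves on stopping (positive dechallenge), K = known response pattern. Each is 1 or 0, giving 2^4 = 16 patterns. 'Must have' is read as 'at least'.

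- Definitely: T = N = K = 1, treating its own item on other causes as N.
- Probably: T + N + D + K ≥ 3.
- Possibly: T + N + D + K ≥ 2.
- Unlikely as written: (1−T) + N + D + (1−K) ≥ 2.
- Unlikely with items 2 and 3 negated: (1−T) + (1−N) + (1−D) + (1−K) ≥ 2.

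**Two examples as written.** With all four facts present, Unlikely scores 0 + 1 + 1 + 0 = 2, so the event meets Definitely, Probably, Possibly and Unlikely. With only fitting timing, Possibly scores 1 and Unlikely scores 0 + 0 + 0 + 1 = 1, so no list is met.

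**All patterns, all four items assessed.**

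| Count | As written | Items 2 and 3 negated |
|---|---|---|
| Probably or Definitely patterns also meeting Unlikely | 3 of 5 (TNDK, TND, NDK) | 0 of 5 |
| Patterns meeting no list | 2 of 16 (T, K) | 0 of 16 |
| Patterns with exactly two pro-causal items also meeting Unlikely | 5 of 6 | 6 of 6 |

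**Direction.** There are 16 single steps that add N or D to a pattern lacking it. As written, 6 of them move the event onto the Unlikely list and none moves it off. After negation, none moves it on and 6 move it off.

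**If 'must have' means 'exactly'.** Overlap with Probably or Definitely is 1 of 5 as written (TNDK) and 0 of 5 after negation.

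**If dechallenge cannot be assessed.** Item 3 is then met in neither polarity, and four patterns reach at least Possibly: TN, TK, NK and TNK. As written, Unlikely is (1−T) + N + (1−K) ≥ 2, giving TN = 2, NK = 2, TNK = 1, TK = 0: overlap 2 of 4. Negated, it is (1−T) + (1−N) + (1−K) ≥ 2, giving 1, 1, 0 and 1: overlap 0 of 4. If there is also no known response pattern (K = 0), only TN reaches Possibly, and the overlap goes from 1 of 1 to 0 of 1.

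**The case against.** The strongest reply is that the item lists do not decide the category. Each category opens with a judgement, the lists say only that an event may be so considered, and the investigator also weighs event type, organ system and onset. Probably calls for a high degree of certainty, so an investigator who sees all four pro-causal items should not choose Unlikely. The CRF, which may carry its own guidance, is not among the documents.

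Safety oversight does not rest on the label alone. SAP 7.4.2 tabulates all adverse events, and protocol 9.4 requires all SAEs to be reported. The safety review committee (SRC) reviews each completed cohort (8.6). Relatedness under stopping criterion g is judged by the SRC, criterion h is based on PK, and study stopping criterion 1 in 5.3 has no causality condition. All of this stands. It lowers the consequence but does not make the two items correct, and the treatment-related tables still use the recorded category.

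A reader might also infer that the missing tie-break between Possibly and Unlikely is a second error. Both need two items and their openings are close. But this is a scale of judgement with a named decision-maker, so an unstated tie-break is a matter for clarification. The overlap that remains after negation also depends on dechallenge being assessed. Part A (24 of 44 participants) is single-dose, so there is no later dose to withhold. If dechallenge is treated as not assessable there, negation alone removes the overlap.

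**Conclusion.** Items 2 and 3 of 'Unlikely related' are wrong as written. With all four items assessed and 'must have' read as 'at least', 3 of 5 Probably or Definitely patterns also meet the Unlikely list and 2 of 16 patterns meet no list; negation brings both to 0.

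A reader might infer that related events will be undercounted or a stopping criterion missed. The documents do not support that. The patterns are not claimed to be equally likely, nothing shows how often investigators would follow the list against their own judgement, and no effect on results is shown. Severity is low: this is an incoherent written criterion with a risk of inconsistent classification.

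**What to change.** In protocol 9.2.3, negate two items of 'Unlikely related' so that all four argue against the drug. Item 2 should say that the participant's condition, surroundings or toxic exposure, or another therapy could readily explain the event. Item 3 should say that the event does not disappear or lessen when treatment is stopped. Carry the text to the CRF guidance and a site memo. SAP 4.3.1 defers to 9.2.3, so the SAP needs only the new protocol version.

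The cost is wording, with no new data or procedures. Classification can shift either way: three patterns leave the Unlikely list (TND, NDK, TNDK) and three join it (T, K, TK), and TK also meets Possibly.

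Optional clarification: when dechallenge is assessed, the 6 of 16 patterns with two items for and two against still meet both Possibly and Unlikely after negation. The sponsor may state whether 'must have' means 'at least' and how such events are classified.

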9.2.4. Treatment Given as a Result of the Event

The event impact in terms of treatment provided will be as either: none, medication administered, non-drug therapy administered, surgery performed, hospitalization, or other (with a specification).

9.2.5. Event Outcome Assessment

The outcome of the event will be assessed as either: fatal, not recovered/not resolved, recovered/resolved, recovered/resolved with sequelae, recovering/resolving, or unknown. Only one AE per participant is allowed to have an outcome assessment as “death.” If there are multiple causes of death for a given participant, only the primary cause of death will have an outcome of death.

9.3. SERIOUS ADVERSE EVENT (SAE) DEFINITION

A SAE is defined as any AE that:

- Results in death
- Is life threatening (the participant is at immediate risk of dying from the adverse experience)
- Requires participant hospitalization or prolongs existing hospitalization
- Results in persistent or significant disability/incapacity
- Is a congenital anomaly/birth defect
- Important medical events that may not result in death, be life-threatening, or require hospitalization may be considered a serious adverse effect when, based upon appropriate medical judgment, they may jeopardize the participant or participant and may require medical or surgical intervention to prevent one of the outcomes listed in this definition.

9.4. REPORTING OF SERIOUS ADVERSE EVENTS (SAEs)

The Investigator is required to report all SAEs that occur during the time period specified in **Section 9.2**. Once the Investigator becomes aware of an SAE, he/she must report the SAE to Safety Contact/Sponsor within 24 hours. The fax number or email address for reporting SAEs can be found in the protocol-specific Safety Management Plan.

The Safety Contact/Sponsor may request additional supporting documentation as it becomes available, such as lab reports, 12-lead ECG reports, discharge summary, hospital notes, etc., if applicable. Additional follow-up information as it becomes available must be reported to the Medical Monitor.

The Investigator is also responsible for reporting all SAEs to the appropriate Institutional Review Board (IRB) in accordance with local laws and regulations. The Investigator is responsible for maintaining documentation in the study file that indicates the IRB has been properly notified.

9.4.1. SAE Follow-Up

All participants experiencing an SAE, including the discontinued participants, must be closely followed until sufficient information is obtained to indicate a return to normal status or until the event stabilizes at a level acceptable to the Investigator or the last study visit, whichever occurs first (i.e., recovery, return to baseline status, no further improvement expected, or death).

For each SAE indicated as an unresolved event on the initial report, regardless of whether the participant completed the study or withdrew, the site should submit a follow-up report with updated information.

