4.4. UNSCHEDULED VISITS

In the event that the participant will return to clinic at a time other than a regularly scheduled study visit, the visit will be regarded as an unscheduled visit. This includes when participants require rescue therapy or need interim care due to chronic illness. Assessments at unscheduled visits are at the discretion of the Investigator. All pertinent findings, including adverse events or changes in medications, will be noted in the CRF.

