5.2. PARTICIPANT WITHDRAWAL

At any point during the study all participants have the right to withdraw without prejudice to future care. Documentation to whether or not each participant completed the clinical study will be recorded. If study treatment is discontinued for any participant, the reason(s) will be documented.

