5.2.1. Participant Discontinuation

The Investigator can discontinue a participant at any time if in their clinical judgment considers to be medically necessary. Investigators considering discontinuing study treatment should contact the medical monitor prior to such discontinuation. Participants who have study treatment discontinued will continue to be followed, per protocol, whenever possible. Participants who have study treatment discontinued due to a serious adverse event will be followed until resolution or stabilization of the event as described in [Section 9.4.1](#) (SAE Follow-Up).

In addition, participants will be discontinued from the study in the following conditions:

- Withdrawal of consent.
- The participant has an AE and is unsuitable for the study as judged by the Investigator.
- The participant experiences events which significantly affect safety, tolerability, or PK profile of the drug, and is unsuitable for the study as judged by the Investigator.
- Participants have poor compliance or major protocol deviations occur is unsuitable for the study as judged by the investigator.
- The Investigator no longer believes participation is in the best interest of the participant.

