9.1. ADVERSE EVENT (AE) DEFINITION

An adverse event (AE) is defined as any unfavorable or unintended sign, symptom, or disease that occurs or is reported by the participant to have occurred, or a worsening of a pre-existing condition. An adverse event may or may not be related to the study treatment.

AEs will be elicited through direct questioning and participant reports. Any abnormality in physical examination findings or laboratory results that the investigator believes is clinically significant (CS) to the research participant and that occurred after initiation of the first study treatment will be reported as AEs. Abnormal findings that are NOT clinically significant should not be recorded as an AE.

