9.2. REPORTING OF ADVERSE EVENTS (AEs)

The Investigator will then record all relevant AE/SAE information in the eCRF. All AEs will be collected from the time of dose administration until the safety follow-up visit. Medical occurrences that occur before the start of the study treatment, but after obtaining the ICF will be recorded in the Medical History section of the eCRF and not in the AE section, unless considered related to the study procedures. All events will be followed to resolution or until the participant completes the study. A final assessment of outcome will be made at that time.

All AEs must be recorded in the participant's medical records and on the CRF. AEs will be reported using customary medical terminology along with the following information: the onset and end dates, whether the event is considered to be a SAE (see [Section 9.3](#)), the impact the event had on study treatment (see [Section 9.2.1](#)), the Toxicity Grading Scale (intensity) of the event (see [Section 9.2.2](#)), the causality of the event (see [Section 9.2.3](#)), whether treatment is given as a result of the event (see [Section 9.2.4](#)), and the outcome of the event (see [Section 9.2.5](#)).

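### Protocol section 9.4.1 lets required follow-up of a serious adverse event stop at the last study visit while the event is neither resolved nor stable

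*Protocol*

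**What the plan says.** Protocol section 9.4.1 covers all participants with an SAE, including discontinued ones. It requires close follow-up until the participant is back to normal, or the event is stable at a level the Investigator accepts, "or the last study visit, whichever occurs first". A bracket at the end of the same sentence explains the endpoints as "recovery, return to baseline status, no further improvement expected, or death". A second paragraph asks the site for an updated report on any SAE that was unresolved when first reported, whether or not the participant finished the study.

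Three other sections bear on the point:

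- Section 5.2.1: participants whose treatment is "discontinued due to a serious adverse event will be followed until resolution or stabilization of the event as described in" section 9.4.1.
- Section 9.2: "All events will be followed to resolution or until the participant completes the study". A final outcome is assigned at that time.
- Tables 4-1 and 4-2 and sections 4.2.6 and 4.3.8: the last scheduled visit is FU2, Day 28 with a window of ±1 day, in both parts.

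**The concern.** The three stopping points in 9.4.1 are joined so that the earliest one applies. Two are clinical and the third is a calendar date. When the date comes first, the duty of close follow-up ends whatever the state of the event. Two sites could read the same sentence differently: one follows to a clinical endpoint because the bracket lists only those, and the other stops on Day 28. Both could cite 9.4.1.

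This is a participant-safety rule in a first-in-human study (section 1.4.2). The SAEs it fails to cover are those still evolving when the schedule runs out. The statistical output is not at stake: an SAE that has started is counted in the SAP section 7.4.2 tables whether or not it is followed further.

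**Working it through.** The plan states no figure for this point, so the check compares the texts and then counts days.

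**Stopping rules side by side**

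| Section | Who or what | Clinical endpoint | Calendar limit |
|---|---|---|---|
| 9.4.1, main clause | every SAE | return to normal, or stable | last study visit, if earlier |
| 9.4.1, bracket | same sentence | recovery, baseline, no further improvement, death | none listed |
| 5.2.1 | treatment stopped for an SAE | resolution or stabilisation | none stated; refers to 9.4.1 |
| 9.2 | all events | resolution | study completion |

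The bracket and the main clause of 9.4.1 do not match. Section 5.2.1 names only clinical endpoints but sends the reader to a section that adds a calendar limit. Section 9.2 agrees with the main clause of 9.4.1, so changing 9.4.1 alone would leave the limit in force there.

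**Days of required follow-up**

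Inputs: last visit on Day 28, window Day 27 to Day 29 (Tables 4-1 and 4-2). Event collection starts at dosing and runs to the safety follow-up visit (section 9.2). I take that visit to be FU2, because footnote 19 of both tables has adverse events followed up on Day 28.

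Formula: maximum required follow-up = 28 − onset day, with range (27 − onset day) to (29 − onset day).

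- Onset Day 7: 28 − 7 = 21 days (20-22)
- Onset Day 14: 28 − 14 = 14 days (13-15)
- Onset Day 21: 28 − 21 = 7 days (6-8)
- Onset Day 27: 28 − 27 = 1 day (0-2)

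**Do other provisions supply the missing duty?**

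- Section 7.8 requires a clinically significant finding to be measured again, at suitable intervals, until the value is acceptable or the cause is diagnosed or otherwise explained. It has no visit limit. It belongs to the laboratory assessments, so it does not reach every SAE.
- Section 5.2.2 asks the site to make every effort to obtain follow-up information on withdrawn participants, and applies the SAE procedures to those withdrawn for an SAE. Those procedures include the 9.4.1 limit.
- Section 4.4 allows unscheduled visits, but "Assessments at unscheduled visits are at the discretion of the Investigator".
- Section 9.4 makes it mandatory to pass later information to the Medical Monitor, and the second paragraph of 9.4.1 asks for an updated report. These are reporting steps. Neither sets a duration, an endpoint or a clinical assessment.

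Together these reduce the gap. None requires clinical follow-up of every SAE to an endpoint.

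**The case against.** The strongest defence is that the limit is deliberate. Sections 9.4.1 and 9.2 agree on it, and the bracket can be read as explaining only the clinical endpoints, leaving the calendar limit intact. That is a fair reading, and it confirms that the limit operates. It gives no reason for applying the limit to an unstable SAE.

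The defence is right on several stronger inferences that a reader might draw:

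- **That 5.2.1 and 9.4.1 flatly contradict each other.** Section 5.2.1 defers to 9.4.1 for its terms and so takes in the limit. This is a mismatch of wording, and it matters mainly in Part B, because Part A is a single dose.
- **That an early leaver's follow-up could end at the early-termination visit.** Section 5.2.1 does allow removal from the study where "The participant has an AE and is unsuitable for the study as judged by the Investigator", and the last study visit is not defined. However, the schedules show FU2 as the final visit. Section 5.2.1 continues follow-up after treatment is stopped where possible, and 5.2.2 asks for every effort. The shorter cut-off is a reading that the text does not state.
- **That laboratory SAEs are left without follow-up.** Clinically significant findings "that occurred after initiation of the first study treatment will be reported as AEs", so 9.2 applies to them, but nothing says that 9.2 overrides 7.8. Section 7.8 counts as a real mitigation.
- **That a probability can be put on the problem.** The documents give no SAE rate and no share of SAEs still open at Day 28, so any such figure would be invented.

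**Conclusion.** The point holds as a gap in a stated safety rule. Section 9.4.1 permits required close follow-up to end at FU2 with an SAE unresolved and unstable, and 9.2 repeats the limit. The later the onset, the shorter the required follow-up, down to 1 day (0-2) for onset on Day 27. This rests on taking the last study visit as FU2 and on event collection running to that visit.

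The situation should be uncommon among screened healthy volunteers, and 7.8, 5.2.2 and the reporting duties soften it. SAE incidence, sample size and the SAP's descriptive tables are unaffected. The change is still worth making, because the rule exists for exactly this case and the correction is short.

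**What to change.** 1. In section 9.4.1, delete "or the last study visit, whichever occurs first". State that SAEs, including those ongoing at the last study visit, are followed until resolution, return to baseline, stabilisation at a level the Investigator accepts, death, withdrawal of consent, or loss to follow-up. Consent withdrawal must stay on the list because of section 5.2: "At any point during the study all participants have the right to withdraw without prejudice to future care".
2. In section 9.2, exempt SAEs from the study-completion limit. The outcome categories in 9.2.5 already allow an event to be recorded as unresolved or resolving at the last visit, and later information can go into SAE follow-up reports.

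Section 5.2.1 then needs no edit.

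Cost: participant contact and reporting after Day 28 in rare cases, plus an amendment that needs IRB approval and may need a consent form update (section 11.3). Scheduled visits, sample size and SAP analyses stay as they are.
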